# Objectives

The current analysis will assess associations of intraoperative hypocapnia with patient demographics, ventilation characteristics, occurrence of intraoperative complications, postoperative pulmonary complications, and length of hospital stay in patients undergoing planned major surgery [3, 9].

### Study design

For this analysis we will use the database of the two randomized clinical trials, named the 'High versus Low Positive End–expiratory Pressure During General Anesthesia for Open Abdominal Surgery (PROVHILO) [3], and the 'PRotective Ventilation with Higher versus Lower PEEP during General Anesthesia for Surgery in OBESE Patients' (PROBESE) [9]. PROVHILO and PROBESE investigated the effects of an open lung approach during low tidal volume ventilation in patients undergoing major surgery.

#### Study details

The full list of inclusion and exclusion criteria of PROVHILO and PROBESE have been reported with the original publications [3, 9]. In short, patients were eligible for participation in the original studies if: (1) planned for major (abdominal) surgery; and (2) at risk for postoperative pulmonary complications. Major exclusion criteria in the original studies were planned thoracic surgery or neurosurgery.

For the purpose of this current analysis, we will additionally exclude patients that underwent unscheduled, i.e., urgent or emergent surgeries, because we consider it likely that these patients may have had metabolic abnormalities at the moment of surgery, i.e., metabolic acidosis, for which the anesthesiologist may have adjusted the intraoperative ventilator settings. This may have led to a 'compensatory' low etCO2. We will also exclude patients for whom etCO2 recordings are missing in the study databases.

#### **Patient categories**

We will use the intraoperatively collected  $etCO_2$  levels to classify patients as either 'with hypocapnia' or 'without hypercapnia', using the cutoff of 35 mmHg. A patient is considered 'hypocapnic' if the  $etCO_2$  was < 35 mm Hg at any point during surgery, from start of the study till end of the study, and classified as 'without hypocapnia' otherwise. In case of a missing value immediately before extubation, we will use the values as reported in the last hour of surgery [10].

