#### Study outcomes

The primary outcome of this analysis is a composite of predefined and collected postoperative pulmonary complications within the first seven days after the surgery, as used in the parent studies. Postoperative pulmonary complications included mild, moderate, and severe respiratory failure; acute respiratory distress syndrome; bronchospasm; new pulmonary infiltrate; pulmonary infection; aspiration pneumonitis; pleural effusions; atelectasis; cardiopulmonary edema; and pneumothorax.

Secondary outcomes include intraoperative complications, a set of intraoperative ventilation parameters, intraoperative vital signs (heart rate, mean

3

arterial pressure, and SpO2) and any new arrhythmias needing intervention. Other endpoints are unexpected need for intensive care unit admission, ICU readmission, and length of stay in hospital up till day 90.

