# Statistical analysis plan

Demographic, clinical and outcome variables are presented as medians with interquartile ranges (IQR), or number with percentage, where appropriate. Differences in baseline characteristics between patients with and patients without hypocapnia will be analyzed using the Pearson Chi–squared or Fisher exact tests for categorical variables and with a one–way ANOVA or Kruskal–Wallis test for continuous variables.

Data points for intraoperative variables (vital signs, ventilator settings and ventilation parameters) will include those collected in the first, second and third hour after start of the study, and before extubation.

Occurrence of postoperative pulmonary complications will be compared using a Fisher's exact test, time to event analyses will be performed using a Cox proportional hazard model or a competing risk model where appropriate. Next, we will perform a propensity matched cohort. Patients will be matched 1:1 with a maximum caliper of 0.02. The following covariates will be used for propensity matching: age, gender, BMI, type of surgery, compliance, history of COPD. We will calculate interaction term for the ARISCAT score as sensitivity analysis. We will perform time-weighted analysis for etCO2 levels in the primary end-points. Kaplan-Meier curve will be used to plot the relation between hypocapnia and the primary outcome.

A LOESS regression will be used to visualize the relationship of etCO2 as a continuous variable with the primary outcome. The association between etCO2 and the primary outcome will be determined using a generalized mixed model in which age, gender, BMI, type of surgery, compliance and history of COPD will be used as covariates. Sankey plot will be used to demonstrate flow association between etCO2 and primary or secondary outcomes.

As a sensitivity analysis the main analyses will be repeated in obese patients and non-obese patients, using a cutoff of 30 kg/m^2 for BMI. Another sensitivity analysis will be performed to determine the effect of PEEP settings on outcome. For this analysis the interaction term for PEEP on the generalized mixed model will be calculated.

A P–value of < 0.05 will be considered statistically significant. All analyses will be performed with R statistics version 4.0.4.

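### One etCO2 value below 35 mmHg makes a patient hypocapnic, so longer operations have more chances to be exposed, and the propensity score omits duration of surgery

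*Combined protocol and SAP*

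**What the plan says.** Under Patient categories, exposure is ever/never: a patient counts as hypocapnic if etCO2 fell below 35 mmHg "at any point during surgery, from start of the study till end of the study, and classified as 'without hypocapnia' otherwise". No minimum number, share or duration of low values is required. The same section adds: "In case of a missing value immediately before extubation, we will use the values as reported in the last hour of surgery".

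The Statistical analysis plan takes intraoperative data points to be "those collected in the first, second and third hour after start of the study, and before extubation". It names vital signs, ventilator settings and ventilation parameters, and does not mention etCO2 there.

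The primary outcome is compared between the two groups with Fisher's exact test and a Kaplan-Meier curve, and then in a matched cohort: "Patients will be matched 1:1 with a maximum caliper of 0.02". The score is specified as follows: "The following covariates will be used for propensity matching: age, gender, BMI, type of surgery, compliance, history of COPD". Etco2 is also related to the primary outcome in a "generalized mixed model in which age, gender, BMI, type of surgery, compliance and history of COPD will be used as covariates". A time-weighted etCO2 analysis is announced in one sentence without further definition. Duration of surgery appears in neither covariate list and in no sensitivity analysis.

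**The concern.** An ever/never rule applied over a window whose length differs between patients gives longer windows more opportunities to be positive. If longer operations also carry a higher risk of pulmonary complications, operation length is related to both exposure and outcome. An association can then appear with no effect of hypocapnia at all.

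The Hypothesis section speaks of an independent association. The matched cohort is the only ever/never comparison for which the plan lists covariates, so that claim leans on what is matched. Type of surgery may stand in for part of duration, but the plan does not show how much.

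**Working it through.** The plan gives no sample size, event rate, frequency of low etCO2 or distribution of operation length. There is no figure to reproduce, and every number below is an illustration on assumed inputs.

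**1. Number of chances.** If etCO2 follows the schedule quoted above, an operation ending within the second hour yields about two readings, one ending within the third hour about three, and a longer one four. The rule for a missing pre-extubation value supports this, because it shows that etCO2 is recorded at that time point.

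**2. Probability of being classed hypocapnic.** Let p be the chance that one reading is below 35 mmHg, ρ the within-patient correlation on a latent normal scale, t = Φ⁻¹(1−p), and k the number of readings. Then

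P(ever) = 1 − ∫ Φ((t − √ρ·u)/√(1−ρ))^k φ(u) du.

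| p | ρ | k = 2 | k = 3 | k = 4 |
|---|---|---|---|---|
| 0.2 | 0.8 | 27.1% | 31.3% | 34.3% |
| 0.2 | 0.3 | 33.4% | 43.0% | 50.3% |
| 0.5 | 0.8 | 60.2% | 65.4% | 68.6% |
| 0.5 | 0.3 | 70.2% | 80.2% | 86.0% |

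**3. Crude odds ratio with no true effect.** For duration classes with share m, exposure probability e and complication risk r, the risk in the exposed is Σmer/Σme and in the unexposed Σm(1−e)r/Σm(1−e).

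*Upper end.* Equal thirds; risks 20%, 32.5%, 45%; p = 0.5; ρ = 0.3.
- Exposed: (0.702×0.20 + 0.802×0.325 + 0.860×0.45)/2.364 = 33.3%.
- Unexposed: (0.298×0.20 + 0.198×0.325 + 0.140×0.45)/0.636 = 29.4%.
- Odds ratio 1.20.

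*Lower end.* Mix 10/20/70%; risks 25%, 32.5%, 40%; p = 0.35; ρ = 0.8, so e = 44.5%, 49.7%, 53.1%.
- Exposed 37.3%, unexposed 36.7%.
- Odds ratio 1.02.

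Over p 0.2–0.5, ρ 0.3–0.8 and both risk gradients:

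| Readings | Mix of duration classes | Crude odds ratio |
|---|---|---|
| 2/3/4 | equal thirds | 1.04–1.20 |
| 2/3/4 | 20/30/50% | 1.03–1.18 |
| 2/3/4 | 10/20/70% | 1.02–1.13 |
| 3/4 only | 50/50 or 30/70% | 1.01–1.06 |

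With N = 2000 (assumed), a nominal 5% test rejects in about one case in three at worst, and in 5–7% when only three or four readings occur. With no risk gradient the odds ratio is 1.00. Fully independent readings, with half the patients at two readings and half at four, would give up to 1.43, but independence within one patient is not a credible input.

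**4. Matched comparison.** This was simulated with 400 replicates, N = 2000, 1:1 nearest neighbour and caliper 0.02. The caliper was taken on the probability scale because the plan names none. Type of surgery was set to identify the duration class in half of patients.

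| Mix | Risks | p, ρ | OR without duration | Rejection | OR with duration | Pairs without → with |
|---|---|---|---|---|---|---|
| thirds | 20–45% | 0.5, 0.3 | 1.15 | 11.5% | 1.00 | 425 → 425 |
| thirds | 20–45% | 0.35, 0.6 | 1.07 | 7.5% | 0.99 | 885 → 862 |
| 10/20/70 | 20–45% | 0.35, 0.6 | 1.05 | 5.5% | 1.01 | 813 → 803 |
| 10/20/70 | 25–40% | 0.35, 0.6 | 1.03 | 4.8% | 1.00 | 812 → 801 |
| 10/20/70 | 25–40% | 0.35, 0.8 | 1.02 | 4.8% | 1.00 | 949 → 931 |

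The Monte Carlo error of a 5% rejection rate is √(0.05×0.95/400), about 1.1 points, so the last three rows are nominal. The value of 1.00 with duration follows from how the model was built and is not evidence that adjustment is safe.

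**5. Direction, and count versus duration.** With classes of 2/3/4/4 readings (mix 10/20/35/35%) and a low-value chance 5–10 points lower in the longest class, the crude odds ratio is 0.94–1.07, so the sign can change. Adjusting only for the number of readings then leaves 0.95–0.99. If the chance is 5–10 points higher in the longest class, it leaves 1.01–1.04. Duration is therefore the better covariate.

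**The case against.** **The effect may be close to nil.** This largely stands. In the settings where most operations are long, the matched comparison rejects at its nominal rate, and the larger figures depend on a sizeable group with only two readings. The Objectives describe planned major surgery, which may contain few such operations.

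**The mechanism rests on inference.** Applying the schedule to etCO2 is an inference. The plan also excludes patients whose etCO2 "recordings are missing in the study databases". If that meant anyone lacking one scheduled value, every patient would have the same number of readings and the artefact would vanish. That reading does not fit the rule that fills in a missing pre-extubation value, since that rule keeps such patients in.

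**Other analyses avoid the artefact.** The mixed model and the LOESS curve appear to use etCO2 itself, and a time-weighted analysis is planned. That is correct for those analyses. They do not replace the ever/never grouping behind the Fisher test, the matched cohort and the Kaplan-Meier curve, and the time-weighted analysis is not defined.

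**Duration is known only at the end of surgery.** If hypocapnia contributes to intraoperative complications and these prolong surgery, matching on duration could remove part of a real effect. This stands, and it is why both matches should be reported.

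A reader might also infer that the mixed model shares the error, because its covariate list is the same. The documents do not support that: having more chances of one low value does not bear on continuous etCO2. Ordinary confounding by duration is possible there, but nothing in the plan demonstrates it.

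**Conclusion.** The omission is real. It matters only for the crude and matched ever/never comparisons of the primary outcome, which cannot be fully separated from operation length as planned. With no true effect and within-patient correlation of 0.3 to 0.8, the assumed inputs give crude odds ratios of about 1.01 to 1.20, usually near the low end, and matched ones of 1.02 to 1.15.

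This rests on three assumptions that the documents do not settle: etCO2 follows the hourly schedule, complication risk rises with duration, and low values are not rarer in long operations. A reader might conclude that the plan is bound to produce a spurious harmful association. The documents do not support that, since the bias may be negligible or reversed. Severity is minor to moderate. Confidence is high that duration is in neither covariate list and low on the size of the bias.

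**What to change.** - **Primary outcome, matched analysis.** Add duration of surgery or of intraoperative ventilation, rather than the number of readings alone, to the propensity score. Report the planned six-covariate match next to it, and state that duration may partly follow from exposure.
- **Sensitivity analysis.** Define the time-weighted etCO2 analysis already announced, or use the proportion of readings below 35 mmHg, as a duration-neutral check on the ever/never result. The ever/never grouping can stay.
- **Intraoperative outcomes.** The plan states: "Secondary outcomes include intraoperative complications, a set of intraoperative ventilation parameters". Do not add duration routinely for the intraoperative complications, because it may be a consequence of them.
- **Mixed model.** Adding duration is optional.

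The cost is one covariate and a few sentences in the Statistical analysis plan, provided that duration is in the pooled database, which the documents do not say. A few matched pairs may be lost (0–3% in the simulation), and the association may shrink.

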#### Study outcomes

The primary outcome of this analysis is a composite of predefined and collected postoperative pulmonary complications within the first seven days after the surgery, as used in the parent studies. Postoperative pulmonary complications included mild, moderate, and severe respiratory failure; acute respiratory distress syndrome; bronchospasm; new pulmonary infiltrate; pulmonary infection; aspiration pneumonitis; pleural effusions; atelectasis; cardiopulmonary edema; and pneumothorax.

Secondary outcomes include intraoperative complications, a set of intraoperative ventilation parameters, intraoperative vital signs (heart rate, mean

3

arterial pressure, and SpO2) and any new arrhythmias needing intervention. Other endpoints are unexpected need for intensive care unit admission, ICU readmission, and length of stay in hospital up till day 90.

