#### Rationale

Lung-protective intraoperative ventilation (LPV) has the potential to improve the outcome of surgery patients through a reduction in postoperative pulmonary complications [1, 2]. Use of intraoperative ventilation strategies that use a low tidal volume could result in intraoperative hypercapnia. However, hypocapnia remains surprisingly common during intraoperative ventilation [3, 4], possibly meaning that anesthesiologists continue to use high, if not too high respiratory rates or tidal volumes.

Previous studies suggested associations between intraoperative derangement of end-tidal carbon dioxide (etCO2) and postoperative outcomes [5, 6]. Indeed, two studies in highly selected patient groups showed associations of intraoperative hypocapnia with prolonged length of hospital stay, in patients undergoing pancreaticoduodonectomy [7], and in patients undergoing hysterectomy [8].

To gain a better understanding of the epidemiology of intraoperative hypocapnia, in particular the associations of intraoperative hypocapnia with patient demographics, ventilator characteristics, and perioperative complications we will perform an Individual patient–level meta–analysis of two recent randomized clinical trials of intraoperative ventilation [3, 9].

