# **Planned inserts**

- Figure 1: CONSORT
- Figure 2: Sankey plots
- Figure 3: distribution plots of ventilation characteristics
- Figure 4: LOESS regressions
- Figure 5: Kaplan-Meier curve
- Table 1: Patient characteristics

Table 2: Intraoperative characteristics, including ventilation and hemodynamic characteristics

Table 3: Comparison of outcomes between the patients with or without hypocapnia

- eTable 1: Patient characteristics for studies
- eTable 2: Ventilation characteristics
- eTable 3: Sensitivity analyses

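### The ever/never hypocapnia label spans the same window as the intraoperative secondary outcomes, so some of those outcomes precede the exposure and the comparison has no direction

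*Combined protocol and SAP*

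**What the plan says.** - **Exposure.** Patient categories gives each patient one fixed label: hypocapnic if etCO2 fell below 35 mm Hg "at any point during surgery, from start of the study till end of the study".
- **Outcomes.** Study outcomes states: "Secondary outcomes include intraoperative complications, a set of intraoperative ventilation parameters, intraoperative vital signs". The same sentence adds new arrhythmias that need intervention.
- **Timing of the data.** In the Statistical analysis plan section, the data points for ventilation variables and for vital signs "will include those collected in the first, second and third hour after start of the study, and before extubation".
- **Comparison.** Under Planned inserts, Table 3 is a "Comparison of outcomes between the patients with or without hypocapnia". Ventilation and hemodynamic characteristics have their own Table 2.
- **Handling of time.** The one provision that weights etCO2 by time is confined to the primary outcome: "We will perform time-weighted analysis for etCO2 levels in the primary end-points". The LOESS curve and the generalized mixed model also concern the primary outcome. The Sankey plots may include secondary outcomes, but no ordering rule is given for them.
- **Aim.** Objectives speaks of "associations of intraoperative hypocapnia with patient demographics, ventilation characteristics, occurrence of intraoperative complications" and gives no direction.
- **The plan's own view of ventilation.** Rationale comments on how common hypocapnia is, "possibly meaning that anesthesiologists continue to use high, if not too high respiratory rates or tidal volumes". Study details excludes unscheduled surgery because adjusted ventilator settings could themselves have produced a low etCO2.

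**The concern.** The label is known only at the end of surgery, but it is compared on variables recorded during surgery. A patient whose only low etCO2 is the one before extubation sits in the hypocapnia group for hour-1 blood pressure and for any arrhythmia in hour 2. If a complication, or the response to it, lowers etCO2 later in the case, the two-group table shows an association that runs from complication to hypocapnia, and the table cannot tell the two directions apart.

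For ventilator settings and vital signs there is a second cost, even if the aim is only to describe. The hypocapnia group pools low and normal readings from the same patients. This blurs the link between etCO2 and ventilation that Objectives sets out to assess. Listing ventilation parameters as outcomes also sits badly with Rationale and Study details, which treat them as drivers of etCO2.

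What is at stake is how the intraoperative results are read. The threshold "A P–value of < 0.05 will be considered statistically significant" would apply to them, and a difference produced by time order could be reported as a complication of hypocapnia.

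**Working it through.** The plan states no sample size, event rate or timing, so there is no figure to reproduce. The fault follows from setting the sections side by side; the numbers only illustrate it.

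**Overlap of windows.** The exposure uses etCO2 from start to end of the study. The hourly variables are taken at hours 1, 2 and 3 and before extubation. Intraoperative complications and arrhythmias fall in the same interval. Any patient whose first low value comes after the first data point therefore contributes readings, and possibly events, that precede exposure.

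**Assumed inputs.** Four etCO2 readings per patient at the planned data points; chance p = 0.30 to 0.40 of a low value at each; latent within-patient correlation 0 to 0.6. None of these values is in the documents.

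**Mixing, independent readings (closed form).**
- Ever hypocapnic: 1 − (1 − p)^4 = 0.760 for p = 0.30 and 0.870 for p = 0.40.
- Share of the group's readings that are hypocapnic: p / ever = 0.30/0.760 = 39% and 0.40/0.870 = 46%.
- Share strictly before the first low value: [p(1−p) + 2p(1−p)² + 3p(1−p)³] / (4 × ever). For p = 0.30 this is 0.8127/3.040 = 27%; for p = 0.40 it is 0.7872/3.482 = 23%.

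Simulation with correlation up to 0.6 extends these to 39-60% hypocapnic and about 17-27% strictly before.

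**Reverse path.** Assume a 20% complication risk, onset spread evenly over the four intervals, per-reading hypocapnia raised from 0.30 to 0.40 or 0.50 from the reading that closes the onset interval, and no effect of hypocapnia on complications. With independent readings:
- No complication: P(never hypocapnic) = 0.7^4 = 0.2401, so the odds of ever being hypocapnic are 0.7599/0.2401 = 3.165.
- Complication, raised to 0.40: P(never) = (0.2058 + 0.1764 + 0.1512 + 0.1296)/4 = 0.1658; odds 5.03; odds ratio 5.03/3.165 = 1.6.
- Complication, raised to 0.50: P(never) = (0.1715 + 0.1225 + 0.0875 + 0.0625)/4 = 0.1110; odds 8.01; odds ratio 2.5.

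A constant hazard of onset, which places events slightly earlier, takes the upper value to about 2.6. Correlated readings take the lower value to about 1.4. The range over correlation 0 to 0.6 is therefore about 1.4-2.6.

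**Same scenario, exposure fixed at the first reading.** One quarter of complications precede it.
- Raised to 0.40: P(low at first reading | complication) = 0.25 × 0.40 + 0.75 × 0.30 = 0.325; odds ratio (0.325/0.675)/(0.30/0.70) = 1.1.
- Raised to 0.50: 0.25 × 0.50 + 0.75 × 0.30 = 0.350; odds ratio (0.350/0.650)/(0.30/0.70) = 1.3.
- If every complication preceded the first reading: (0.40/0.60)/(0.30/0.70) = 1.6 and (0.50/0.50)/(0.30/0.70) = 2.3. First-reading exposure then gives little protection.

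**The case against.** The strongest reply is that the plan claims association, not effect. Hypothesis and Objectives place ventilation variables beside patient demographics, which cannot result from hypocapnia, so the list carries no direction. Planned inserts puts ventilation and hemodynamics in Table 2, apart from the outcome comparison in Table 3. This largely stands. A reader might infer that the plan treats respiratory rate and tidal volume as effects of hypocapnia; that reading rests mainly on the word outcomes in Study outcomes, and Rationale and Study details say the opposite. For these variables the remaining faults are the listing as outcomes and the blurring of the association.

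A reader might also infer that most or many intraoperative outcomes precede exposure. The documents do not say when hypocapnia first occurs, so this cannot be shown. Under the assumptions above, about 17-27% of the group's readings do.

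Nor is the odds ratio of 1.4-2.6 a prediction of bias. The complication rate, the rise in hypocapnia and the reverse path itself are all assumed. No section says that complications lower etCO2.

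What the objection does not remove is the ordering question for intraoperative complications and arrhythmias. Calling the result an association does not tell the reader that some events came first, and matching on the listed covariates cannot restore time order.

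**Conclusion.** The point holds, limited to the intraoperative secondary outcomes. The exposure label draws on the whole operation, its comparators come from the same period, and no rule orders them. The overlap is plain in the text. Its size is not known: 39-60% hypocapnic readings, 17-27% of readings before first hypocapnia, and a spurious odds ratio of about 1.4-2.6 all depend on assumed rates, correlation and timing.

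It would be wrong to infer that the main result is compromised. Postoperative pulmonary complications within seven days, the ICU endpoints and length of stay follow the exposure window and do not share this fault. The change is one that should be made; it does not undermine the study.

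**What to change.** 1. **Ventilation variables and vital signs.** Analyse them reading by reading against etCO2 at the same reading, in a mixed model with a patient random intercept and time. Present ventilator settings as determinants or correlates of hypocapnia and remove them from the list of outcomes. Lagged etCO2 for vital signs is optional; no section supports a delayed effect.
2. **Intraoperative complications and new arrhythmias.** Add an analysis with exposure fixed by first-hour etCO2. Count only later events if event times were recorded; the plan should say whether they were.
3. **Ever/never comparison.** Keep it, but report it as concurrent association without direction.

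The cost is a few more models. The plan shows that hourly ventilation and vital-sign data are held, and its rule for a missing value before extubation implies repeated etCO2 values; that these fall at the same data points should be confirmed. First-hour exposure discards later etCO2 information and so gives less precision for rare complications. Without event times, it reduces reverse effects but does not remove them.
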